7.3. IP Storage

The shelf life of STI-5656 is at least 3 years when stored at room temperature (approximately 20° to 25°C [68° to 77°F]).

7.4. IP Accountability

The Principal Investigator (or designee) is responsible for accountability of all used and unused IP at the site.

The IP provided by the Sponsor must be made available for inspection by the Sponsor or its representatives and regulatory agency inspectors upon request.

7.5. IP Handling and Disposal

The Investigator must keep an accurate accounting of the number of bottles and capsules of STI-5656 delivered to the site, administered to subjects, and returned to the Sponsor/Sponsor representative or other disposition during and at the completion of the study.

The IP must be dispensed to subjects only by an appropriately qualified person. The IP is to be used in accordance with the protocol by subjects who are under the direct supervision of the Investigator. Investigators should maintain records that document adequately that the subjects were provided the doses specified by the protocol and reconcile all IP received at the site before final disposition.

All IP, including unused, partially used, and empty containers, should be disposed of in accordance with federal, state and local regulations and the institutional standard operating procedures (SOPs) or returned to the Sponsor/Sponsor representative as directed if destruction at the site is not possible.

8. STUDY PROCEDURES

Study procedures will be performed as described in the Schedule of Assessment [Table 1](#).

Additional unscheduled visit/assessments may be performed at any time if clinically indicated and will be captured in the eCRFs if performed.

Protocol waivers or exemptions are not allowed, with the exception of immediate safety concerns. Such concerns should be discussed with the Sponsor immediately upon occurrence or awareness to determine if the subject should continue or discontinue the IP (subjects in Treatment Arm 1). Adherence to the study design requirements, including those specified in the Schedule of Assessments, is essential and required for study conduct.

All screening evaluations must be completed and reviewed to confirm that potential subjects meet all eligibility criteria. The Investigator will maintain a screening log to record details of all subjects screened and to confirm eligibility or record reasons for screening failure, as applicable.

A subject may be re-screened once for the study if the defined screening period has been exceeded and the subject has not been randomized in the study.

8.1. Description of Procedures

8.1.1. Informed Consent

All subjects will review and sign an IRB-approved Informed Consent Form prior to performing any procedures specifically for this study.

8.1.2. RT-PCR assay for SARS-CoV-2

If RT-PCR confirmation of SARS-CoV-2 is not within 7 days prior to planned randomization, then positive RT-PCR test results more than 7 days prior to randomization is allowed to confirm eligibility if the site is unable to obtain a repeat sample and if the subject has progressive disease consistent with COVID-19.

8.1.3. Collection of Demographics, Medical History, Prior and Concomitant Medications

Demographics include age, sex, race, ethnicity, date of birth.

Current (active) medical conditions and relevant (non-active) medical history. Details of COVID-19 history should include COVID-19-related symptoms, time of onset of symptoms, date of first positive COVID-19 test result

Concomitant medications and prior medications taken within 28 days of informed consent

8.1.4. Vital Signs

Vital signs include body temperature (F), respiratory rate, radial pulse rate, systolic and diastolic blood pressure, and oxygen saturation (pulse oximetry). Pulse and blood pressure should be taken with subject in at least in a semi-recumbent position.

It is preferred to collect vital signs at approximately mid-afternoon each day. Vital signs may be obtained at additional times as deemed necessary by the Investigator.

8.1.5. Physical Exam

A physical exam should be performed at Screening and at hospital discharge or Early Termination Visit, whichever is later. Height (at screening) and weight (screening and discharge) should be recorded also.

8.1.6. 12-lead Electrocardiogram (ECG)

A 12-lead ECG is to be performed during Screening, between 2 and 4 hours after study drug dosing and at any time a subject complains of anything suggestive of a cardiac abnormality.

8.1.7. Clinical laboratory tests

Serum chemistry, hematology, coagulation, urinalysis and urine pregnancy tests are to be performed locally.

8.1.7.1. Serum Chemistry

Albumin, alkaline phosphatase (ALP), alanine aminotransferase (ALT), aspartate aminotransferase (AST), bicarbonate, total bilirubin (TBIL), blood urea nitrogen (BUN), calcium, chloride, creatinine, glucose, potassium, sodium, total protein, D-dimer, fibrinogen.

8.1.7.2. Hematology

Hemoglobin, hematocrit, red blood cell (RBC) count, RBC indices, mean corpuscular hemoglobin, mean corpuscular hemoglobin concentration, platelet count (or estimate), and white blood cell count including differential.

8.1.7.3. Coagulation

International normalized ratio (INR), PTT.

8.1.7.4. C-reactive protein, serum ferritin, absolute lymphocyte count and cytokines

Blood should be collected for measuring C-reactive protein (CRP), serum ferritin, VEGF-A, and cytokines (IL-6, TNF- α , IFN γ , IL1 β , IL-7, IL-8, IL-10, IL-12, IL-17, IL-18, IP10) should be measured on Days 3, 5, 7, 10, 14 and 28.

8.1.7.5. Urinalysis

Urinalysis to be performed locally. Urinalysis includes protein, glucose, and blood (microscopic) – red blood cells per high power field (rbc/hpf).

8.1.7.6. Urine Pregnancy Test

Urine pregnancy tests (B-HCG) will be performed (locally) for women of childbearing potential. FSH tests may be performed to confirm a woman is of non-childbearing potential if the subject is not on hormonal replacement therapy or not surgically sterile (refer to eligibility criteria for details).

8.1.8. Respiratory Status

Record FiO2 (and PaO2) at the time of arterial blood gas sampling. If PaO2 is not available, use SpO2. Other respiratory status data to collect includes oxygen supplementation status: mechanical ventilation, face mask, nasal cannula or room air. Radiographic findings will also be collected.

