¹²Record FiO₂ (and PaO₂) at the time of arterial blood gas sampling. If PaO₂ is not available, use SPO₂. Other respiratory status data to collect includes oxygen supplementation status: mechanical ventilation, face mask, nasal cannula or room air. Radiographic findings will also be collected.

¹³AEs will be collected from the time of informed consent to Day 60. Any ongoing AEs at Day 28 will be followed until resolution or stabilization.

¹⁴An 8-category ordinal scale of patient health status ranges: 0=no clinical or virological evidence of infection; 1=no limitation of activities; 2=limitation of activities; 3=hospitalized, no oxygen therapy; 4=oxygen by mask or nasal prongs; 5=non-invasive ventilation or high-flow oxygen; 6=intubation and mechanical ventilation; 7=ventilation + additional organ support – pressors, rapid response team (RRT), extracorporeal membrane oxygenation (ECMO); 8=death. See [Section 14.2](#) for form.

¹⁵STI-5656 or placebo administration up to Day 14 or hospital discharge, whichever is sooner for subjects in Treatment Arm 1. Study drug capsules should be taken orally with 200-250 mL of water following at least 2 hours of fasting.

¹⁶Samples will be collected from the first 20 subjects enrolled. Sampling timepoints are as follows: Day 1 (predose) and at 0.5, 1, 2, 4, 8, 12, postdose on dosing days 1 and 8.

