3.2.2. Secondary Endpoints

- Types, frequencies, and severities of AEs and the relationships of AEs to IP; includes serious adverse events SAEs
- Proportion of subjects alive and free of respiratory failure at Day 60
- Change in clinical status (on a 0-8-point ordinal scale²) of subject at Day 7, Day 14, and Day 28
- Proportion of subjects alive and discharged from ICU at Days 14 and 28

² 8-category ordinal scale of patient health status ranges: 0=no clinical or virological evidence of infection; 1=no limitation of activities; 2=limitation of activities; 3=hospitalized, no oxygen therapy; 4=oxygen by mask or nasal prongs; 5=non-invasive ventilation or high-flow oxygen; 6=intubation and mechanical ventilation; 7=ventilation + additional organ support – pressors, rapid response team (RRT), extracorporeal membrane oxygenation (ECMO); 8=death.

- Time from randomization to first occurrence of respiratory failure or death on study due to any cause up to Day 28
- Percent change from baseline in CRP at Days 3, 5, 7, 10, 14, 28
- Relative change from baseline in oxygenation index (PaO₂/FiO₂) up to Day 5
- All-cause mortality at Day 60 and Day 90
- Number of days alive and free of respiratory failure at Day 28
- Number of days with respiratory failure up to Day 28
- Number of days hospitalized up to Day 28
- Number of days in ICU (length of stay) up to Day 90
- Number of days alive outside of hospital up to Day 28
- Number of days alive outside of hospital up to Day 90
- To assess the pharmacokinetic profile in the study population

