## **7.0 GENERAL STATISTICAL CONSIDERATION AND DEFINITIONS**

### **7.1 Baseline and Visit Windows**

Unless otherwise specified, baseline, which is defined as the last non missing assessment prior to the first dose of the study treatment, will be used in baseline and change from baseline analyses. Analyses will be performed according to the scheduled visits.

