### 9.2.3 Continuous Endpoints

For the following continuous endpoints, descriptive statistics will be presented by treatment group and study day. The changes or percent changes from baseline to each subsequent day will be calculated for each subject and descriptive statistics will be presented. Treatment differences between groups will be assessed using a mixed-effects model for repeat measures (MMRM). The model will include group, study day as fixed effects, baseline value as a covariate, interaction between study day and group, interaction between study day and baseline, and subject as a random effect.

- Percent change from baseline in C-reactive protein (CRP) at Days 3, 5, 7, 10, 14, 28
- Relative change from baseline in oxygenation index (PaO2/FiO2) up to Day 5

For each “number of days” endpoint listed below, descriptive statistics will be presented by treatment group. Treatment differences between groups will be assessed using analysis of variance (ANOVA) model with group as a fixed effect.

- Number of days alive and free of respiratory failure at Day 28

- Number of days with respiratory failure up to Day 28
- Number of days hospitalized up to Day 28
- Number of days in intensive care unit (ICU) (length of stay) up to Day 90
- Number of days alive outside of hospital up to Day 28
- Number of days alive outside of hospital up to Day 90

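### The instruction to use SpO2 when PaO2 is missing, with no conversion, source flag or same-source rule, lets the PaO2/FiO2 change up to Day 5 mix mmHg with a percentage

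*Protocol*

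**What the plan says.** Protocol 3.2.2 lists as a secondary endpoint "Relative change from baseline in oxygenation index (PaO₂/FiO₂) up to Day 5". On collection, Protocol 8.1.8 (Respiratory Status) says "Record FiO2 (and PaO2) at the time of arterial blood gas sampling" and then "If PaO2 is not available, use SpO2". Footnote 12 of the Schedule of Assessments has the same instruction, "If PaO₂ is not available, use SPO₂", and the SAP reproduces that footnote in its Appendix 1.

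SAP 9.2.3 takes "Relative change from baseline in oxygenation index" as a continuous endpoint and compares the arms by MMRM: "The model will include group, study day as fixed effects, baseline value as a covariate", plus the interactions of study day with group and with baseline. SAP 7.1 defines baseline as "the last non missing assessment prior to the first dose of the study treatment". SAP 7.3 leaves missing values unimputed unless something else is specified. SAP 10.3 sends respiratory status data to a listing.

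Neither document gives a conversion from SpO2 to PaO2, a separate SpO2/FiO2 variable, a flag for the source of the value, a rule that baseline and follow-up share a source, or a sensitivity analysis restricted to measured PaO2.

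**The concern.** PaO2 is a pressure in mmHg, and SpO2 is a percentage that cannot exceed 100. They are not interchangeable as numerators of the same ratio. If one stands for the other without conversion, a subject whose source changes after baseline acquires a change score that partly reflects the change of units.

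A change of source is plausible. The schedule has no row for arterial blood gas sampling, so sampling follows local practice, while respiratory status is collected daily in hospital. Under the SAP's baseline definition either measure could serve as baseline. Every post-baseline day up to Day 5 is exposed, and a mixed-source baseline also enters the model as covariate and in the baseline-by-day term.

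At stake is the interpretation of one secondary endpoint: the within-arm changes, and the arm comparison if blood gas sampling stops at different rates in the two arms.

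**Working it through.** The plan gives no effect size, SD or power for this endpoint, so there is no figure of its own to reproduce.

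**Formula.** Let P0 and P1 be PaO2 at baseline and follow-up, and S1 be SpO2 at follow-up. With constant FiO2, the denominator cancels:

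- true relative change = P1/P0 − 1
- mixed-source change (PaO2, then SpO2) = S1/P0 − 1
- error = (S1 − P1)/P0

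For an unchanged patient (P1 = P0 = P) the false change is S/P − 1, or P/S − 1 if SpO2 came first.

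**Inputs.** The PaO2-SpO2 pairs are an assumption, not taken from the documents. They come from a standard dissociation equation, S = 100/(1 + 23400/(P³ + 150P)), which gives 65 → 92.4, 70 → 93.8, 90 → 96.9 and 120 → 98.7.

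**Individual subjects, PaO2 at baseline and SpO2 at follow-up.**

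| PaO2 baseline → follow-up (mmHg) | SpO2 used at follow-up | True change | Mixed-source change | Error (percentage points) |
|---|---|---|---|---|
| 65 → 65 | 92.4 | 0% | 92.4/65 − 1 = +42% | +42 |
| 70 → 70 | 93.8 | 0% | 93.8/70 − 1 = +34% | +34 |
| 65 → 90 | 96.9 | 90/65 − 1 = +38% | 96.9/65 − 1 = +49% | about +11 |
| 120 → 120 | 98.7 | 0% | 98.7/120 − 1 = −18% | −18 |

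The sign turns where PaO2 in mmHg equals SpO2 in percent, at about 97 mmHg on this equation.

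**Range without the equation.** Taking SpO2 90-95% and PaO2 60-75 mmHg as free assumptions, an unchanged patient shows +20% (90/75) to +58% (95/60) when PaO2 is followed by SpO2, and −17% (75/90) to −37% (60/95) in the reverse order.

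**Arm level.** Mean false difference = artefact × difference in switching share. With no true effect and an assumed artefact of +40%, SD 30% and 40 per arm, a simulated two-sample t-test (a simplification of the MMRM) gives:

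| Share switching (arm 1 vs arm 2) | False difference (points) | Rejection rate at nominal 5% |
|---|---|---|
| 30% vs 30% | 0 | about 5% |
| 50% vs 30% | 0.40 × 0.20 = 8 | about 17% |
| 60% vs 30% | 0.40 × 0.30 = 12 | about 32% |

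The documents support none of these switching shares in particular. The table shows only that the comparison is harmed by unequal switching and not by equal switching.

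**Same source at both times.** An unchanged patient at constant FiO2 then shows 0%, whichever measure is used.

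**The case against.** The strongest reply is that Protocol 8.1.8 is a data-collection instruction. It does not say that SpO2 is divided by FiO2, and the SAP names only PaO2/FiO2. The SAP overrides the protocol's high-level analysis plan (SAP 1.0), does not impute unless specified (SAP 7.3), and otherwise only lists respiratory status data (SAP 10.3). On that reading a missing PaO2 stays missing and no artefact arises.

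Part of this stands: nowhere does the SAP explicitly put SpO2 into the ratio, so a reader should not infer that the plan certainly computes a wrong value. But this ratio is the only planned inferential use of PaO2, and the SAP's own appendix repeats the instruction. Substitution is therefore the natural reading, and the other reading is equally unstated.

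A reader might also apply the 34% to 42% to patients whose blood gases stop because they are improving. Those figures belong to patients who have not improved. The error depends on PaO2 at follow-up, and the 65 → 90 example shows how far it shrinks. Nor do the documents support a specific bias between arms. A figure of 7 to 8 points (0.20 × 34% to 42%) needs an assumed 20-point imbalance in switching.

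Finally, analysing SpO2/FiO2 in everyone is not a complete answer under present collection. FiO2 recording is tied to blood gas sampling, and the vital signs in Protocol 8.1.4 include pulse oximetry but not FiO2.

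**Conclusion.** The concern holds in this form: following the stated instruction, with no derivation rule in the SAP, lets a percentage and a pressure enter the same change score for any subject whose source changes between baseline and a day up to Day 5. That scales can be mixed follows from the text. The size of the artefact does not; it rests on assumed PaO2-SpO2 pairs and constant FiO2, and both its magnitude and its sign depend on PaO2.

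How often sources would change is unknown. Equal switching shifts both arm means and adds noise without biasing the difference; only unequal switching biases it. A reader might infer that the trial's main result is at risk, but the primary endpoint and its sample size do not use this ratio. This is a correction that should be made to one secondary endpoint.

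**What to change.** In SAP 9.2.3:

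- State that SpO2 is never entered as PaO2. Hold SpO2 as its own variable, with a flag for the source of each oxygenation value.
- Compute each change score only when baseline and follow-up use the same measure. A missing PaO2 stays missing in the MMRM.
- Add relative change in SpO2/FiO2 as a separate analysis.

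In Protocol 8.1.8 and footnote 12 (and the SAP appendix copy), replace the substitution with an instruction to record SpO2 separately and to record FiO2 with each SpO2.

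The cost is one derivation rule, one flag, one added analysis, a footnote amendment, and FiO2 recording on days without a blood gas. There are two statistical downsides. SpO2/FiO2 is insensitive at high saturations: on the equation above, PaO2 rising from 60 to 80 mmHg (+33%) moves SpO2 only from 90.6% to 95.7%, about +6%. And the PaO2-only analysis keeps subjects who still had blood gases, probably the sicker ones and possibly in different proportions by arm, so it should be read alongside SpO2/FiO2.

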3.2. Endpoints

3.2.1. Primary Endpoint

- Proportion of subjects alive and free of respiratory failure at Day 28

Respiratory failure, is defined based on resource utilization of any of the following modalities:

- Noninvasive positive pressure ventilation or continuous positive airway pressure
- Endotracheal intubation and mechanical ventilation
- Oxygen delivered by high-flow nasal cannula (heated, humidified, oxygen delivered via reinforced nasal cannula at flow rates >20 L/min with fraction of delivered oxygen ≥ 0.5)
- Extracorporeal membrane oxygenation

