8.1.9. Clinical status using 8-category ordinal scale of patient health status

An 8-category ordinal scale of patient health status ranges will be used to collect subject clinical status where

- 0 = no clinical or virological evidence of infection;
- 1 = no limitation of activities;
- 2 = limitation of activities;
- 3 = hospitalized, no oxygen therapy;
- 4 = oxygen by mask or nasal prongs;
- 5 = non-invasive ventilation or high-flow oxygen;
- 6 = intubation and mechanical ventilation;
- 7 = ventilation + additional organ support – pressors, rapid response team (RRT), extracorporeal membrane oxygenation (ECMO);
- 8 = death.

See [Section 14.2](#) for form.

8.1.10. IRT Registration, Randomization and Study Discontinuation or Completion.

Subjects will be registered in IRT after signing informed consent and will be randomized using the IRT on Day 1 to either Treatment Arm 1 (STI-5656 plus SOC) or Treatment Arm 2 (placebo plus SOC) using central integrated response technology (IRT). Subject study discontinuation or study completion should also be registered in the IRT.

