## **9.0 EFFICACY EVALUATION**

### **9.1 Primary Endpoint**

The primary efficacy endpoint is the proportion of subjects alive and free of respiratory failure at Day 28, where respiratory failure, is defined based on resource utilization of any of the following modalities:

- Noninvasive positive pressure ventilation or continuous positive airway pressure
- Endotracheal intubation and mechanical ventilation
- Oxygen delivered by high-flow nasal cannula (heated, humidified, oxygen delivered via reinforced nasal cannula at flow rates  $>20$  L/min with fraction of delivered oxygen  $\geq 0.5$ )
- Extracorporeal membrane oxygenation

The number and percentage of subjects will be presented by treatment group using FAS population. Primary analysis to evaluate the differences between groups will utilize a

generalized linear mixed model, assuming a binomial distribution and a logit link. The model will include group as a fixed effect. Subjects who discontinue the study prior to Day 28 will be considered treatment failures.

Sensitivity analyses may be performed using PP population.

After 40 subjects have been enrolled and completed Day 28, an interim futility analysis will be performed to examine the proportion of subjects alive and free of respiratory failure at Day 28. The interim analysis is a non-binding analysis. See Section 7.4 for details.

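### The respiratory data the protocol lists for daily collection cannot apply the primary endpoint's high-flow criterion, because no flow rate is listed and ordinal score 5 mixes failures with non-failures

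*Protocol*

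**What the plan says.** The primary endpoint is "Proportion of subjects alive and free of respiratory failure at Day 28" (Protocol 3.2.1; SAP 9.1). Respiratory failure means use of any of four supports:

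- "Noninvasive positive pressure ventilation or continuous positive airway pressure";
- "Endotracheal intubation and mechanical ventilation";
- high-flow nasal cannula, but only at "flow rates >20 L/min with fraction of delivered oxygen ≥ 0.5";
- ECMO.

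Two respiratory records are scheduled at screening, on Day 1, daily until discharge, and at discharge or early termination (Protocol Table 1 and 8.2).

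- **Respiratory status** (8.1.8, repeated in Table 1 footnote 12 and SAP Appendix 1): "Other respiratory status data to collect includes oxygen supplementation status: mechanical ventilation, face mask, nasal cannula or room air". FiO2 and PaO2 are recorded "at the time of arterial blood gas sampling. If PaO2 is not available, use SpO2".
- **Ordinal scale** (8.1.9): "5 = non-invasive ventilation or high-flow oxygen", then 6 for intubation with mechanical ventilation, 7 for ventilation with added organ support such as ECMO, and 8 for death.

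SAP 9.1 repeats the four-part definition without naming the variables from which failure is derived. SAP 10.3 sends respiratory status to a subject listing only.

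**The concern.** The definition sets a numerical threshold for one of its four components, and the listed data do not contain the numbers needed to apply it. A patient on qualifying high-flow oxygen and one on sub-threshold high-flow oxygen (15 L/min, say, or an oxygen fraction of 0.4) can carry identical entries: nasal cannula in one record, score 5 in the other. The first is a failure under 3.2.1 and the second is not.

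Two programmers could then build different primary endpoints from the same database, and neither would be implementing the stated definition. The futility analysis (SAP 7.4), time to first respiratory failure (9.2.4), the respiratory-failure day counts (9.2.3) and the Day 60 proportion (9.2.1) use the same definition. If flow was not collected, the statistician cannot restore it at analysis.

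These patients can be in the trial. Entry requires saturation below 94% on room air or any supplemental oxygen (5.1), and no exclusion in 5.2 removes patients on high-flow oxygen or non-invasive ventilation.

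**Working it through.** **1. Map each defining support to the scheduled fields.**

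| Support in the endpoint | Respiratory status, 8.1.8 | Ordinal scale, 8.1.9 |
|---|---|---|
| NIPPV or CPAP | not named | score 5 for non-invasive ventilation, shared with high-flow; CPAP not named |
| Intubation with mechanical ventilation | mechanical ventilation | score 6 |
| High-flow cannula above the threshold | at best nasal cannula; no flow | score 5, shared with non-invasive ventilation and sub-threshold high-flow |
| ECMO | not named | score 7 when ventilated |

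Scores 6 to 8 are failures and scores 0 to 4 are non-failures. Score 5 is mixed. Reading the two records together helps: score 5 with nasal cannula suggests high-flow cannula, and score 5 with mechanical ventilation suggests non-invasive ventilation. Score 5 with face mask stays ambiguous. No combination shows whether a high-flow patient exceeded 20 L/min.

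**2. Check the two halves of the threshold.** No section lists a flow rate. FiO2 is tied to arterial sampling, and Table 1 has no row for blood gases. Where FiO2 happens to be recorded below 0.5, the criterion is ruled out. At 0.5 or above, flow still decides.

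**3. Reproduce the plan's sample size.** Inputs from Protocol 9.2: success 0.957 and 0.70, two-sided alpha 0.05, power 80%. The mean p̄ is 0.8285 and d = 0.257.

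- Uncorrected: n′ = [1.96√(2p̄(1−p̄)) + 0.842√(p₁(1−p₁) + p₂(1−p₂))]² / d² = (1.96 × 0.5331 + 0.842 × 0.5011)² / 0.0660 = 32.6.
- Continuity-corrected: n = (n′/4)[1 + √(1 + 4/(n′d))]² = 39.97, so 40 per arm, as stated.
- Power at 40 per arm by the same corrected formula is 80.0%; SAP 7.4 gives 80.8%.

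**4. Size the over-call if every score 5 is a failure.** Let f be the true failure rate (0.043 active, 0.30 placebo) and o the share of true non-failures on sub-threshold high-flow oxygen who are counted as failures, equal in both arms. The observed rate is f + o(1 − f), so the difference becomes 0.257 × (1 − o). For o = 5%:

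- active: 0.043 + 0.05 × 0.957 = 0.091;
- placebo: 0.30 + 0.05 × 0.70 = 0.335;
- difference: 0.244.

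Power is summed exactly over both binomials (40 per arm), rejecting when (|x₁ − x₂|/40 − 1/40) / √(2p̄(1−p̄)/40) ≥ 1.96, where x₁ and x₂ are the observed failure counts and p̄ is the pooled observed rate. By exact summation the baseline is 82.3%, slightly above the formula's 80.0%.

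| o (assumed) | Active failures | Placebo failures | Difference, points | Power |
|---|---|---|---|---|
| 0 | 4.3% | 30.0% | 25.7 | 82% |
| 1% | 5.3% | 30.7% | 25.4 | 79% |
| 2% | 6.2% | 31.4% | 25.2 | 76% |
| 5% | 9.1% | 33.5% | 24.4 | 68% |
| 10% | 13.9% | 37.0% | 23.1 | 58% |

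The difference shrinks only modestly. Most of the power loss comes from the larger variance as the active-arm failure rate moves away from zero. Without the continuity correction, power is 91.5% at baseline, 79.3% at 5% and 67.8% at 10%, so the pattern does not depend on that choice.

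**The case against.** A reader might infer from 8.1.8 that three of the four supports go unrecorded, that qualifying high-flow and CPAP patients would be counted as successes, and that the primary endpoint cannot be derived at all. The documents do not support that. The 8.1.8 list is not the only daily record. The ordinal scale is scheduled for the same days and picks out intubation, ventilated ECMO, and non-invasive ventilation or high-flow oxygen as a group. Missing those failures would require ignoring a same-day score of 5, and nothing in the SAP says to do so. No power loss from missed failures is therefore claimed.

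Three further points are fair.

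- The 8.1.8 list is introduced as what the data include, so it need not be exhaustive, and the eCRF may hold modality, flow and FiO2 fields. This stands as a limit on the finding: it concerns what the protocol requires. A site that follows the written list would not collect flow.
- The SpO2 substitution in 8.1.8 can be read as allowing an FiO2 entry without a blood gas, and the oxygenation-index endpoint implies that FiO2 is wanted. This stands in part. The text replaces PaO2 and does not say that FiO2 is due when no gas is drawn. Daily FiO2 would still leave flow unknown.
- The over-call shares are assumed, and at 1% to 2% the loss is only a few points. This stands, which is why the small values are shown beside the larger ones.

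**Conclusion.** The concern holds for the high-flow criterion and the missing derivation rule. On the fields the protocol lists, death, intubation and ventilated ECMO can be identified. The split within score 5 cannot be made reliably, so the threshold in the endpoint definition cannot be applied.

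If every score 5 is taken as a failure, power falls from 82% to between 79% and 58% as the over-called share rises from 1% to 10% of true non-failures. These figures assume the plan's own success rates, the same share in both arms, and a continuity-corrected comparison of proportions in place of the planned logit model. The documents give no information on the true share, so the table shows sensitivity and is not a forecast. The finding concerns data collected before discharge, and it would narrow or fall away if the eCRF already captures flow and FiO2 for high-flow use.

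**What to change.** In Protocol 8.1.8, Table 1 footnote 12 and SAP Appendix 1, replace the category list with one that matches the endpoint, and record the highest support used each day:

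- room air;
- low-flow cannula or mask;
- high-flow nasal cannula, with flow in L/min and FiO2;
- NIPPV or CPAP;
- intubation with mechanical ventilation;
- ECMO.

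Require FiO2 for high-flow use whether or not a blood gas is drawn. In SAP 9.1, add a sentence stating that respiratory failure is derived from these fields and not from an ordinal score of 5 or more. If the eCRF already holds the fields, cite them there and align the protocol text.

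The cost is protocol wording, a few eCRF fields and a small amount of daily data entry from the bedside chart. No new procedure is needed.
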